5.6 Registration to Companion Studies

There are two substudies within CALGB 30610. The correlative science study must be offered to all patients enrolled on CALGB 30610; the quality of life study must be offered to all English-speaking patients enrolled on CALGB 30610 (although patients may opt to not participate). These substudies do not require separate IRB approval. **Note: The quality of life substudy, CALGB 70702, closed to accrual on August 30, 2017. Therefore, no further patients will be enrolled on the quality of life substudy.**

The substudies included within CALGB 30610 are:

- CALGB 150712: Correlative Science Studies in CALGB 30610 ([Section 10.1](#))
If a patient answers "yes" to "My specimen(s) may be used for the research described above" question #1 in the model consent, they have consented to participate in the substudy described in [Section 10.1](#). The patient should be registered to CALGB 150712 at the same time they are registered to the treatment trial (30610). Samples should be submitted per [Section 6.3](#).
- CALGB 70702: Quality of Life Studies in CALGB 30610 ([Section 10.2](#))

As of August 30, 2017, accrual to CALGB 70702 has been met. **Therefore, after August 30, 2017, not further patients will be registered to CALGB 70702.**

Only English-speaking patients may participate in the QOL companion. If a patient answers “yes” to “I choose to take part in the Quality of Life study and agree to complete the Quality of Life questionnaires” question #5 in the model consent, they have consented to participate in the substudy described in Section 10.2. The patient should be registered to CALGB 70702 at the same time they are registered to the treatment trial (CALGB 30610).

Note: Patients that are registered on CALGB 30610 after they receive one cycle of chemotherapy are NOT eligible for the companion studies.

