The trial is designed to have adequate power to test the null hypothesis $H_0: \log(\lambda_1 / \lambda_{2/3}) = 0$ versus the alternative hypothesis $H_a: \log(\lambda_1 / \lambda_{2/3}) \geq 1.3$ for the comparison of overall survival between the remaining experimental arm (arm 2) and the standard arm (arm 1). The power analysis is based on the following assumptions: (1) the 2-year overall survival rate of the remaining experimental arm (arm 2) is 57.3% and that of arm A is 48.5%. Under exponential survival distribution, the median survival for the remaining experimental arm is 29.9 months and for the standard arm is 23 months, or a hazard ratio of 1.3 (λ_1 / λ_2) for the standard arm to the remaining experimental arm; (2) an accrual length of 6 years; (3) 303 eligible patients in the standard arm and 303 eligible patients in the remaining experimental arm; (4) additional follow-up of 2.5 years after the last enrollment; (5) a two-sided significance level of 0.05. Under these assumptions, at the time of final analysis, at least 483 deaths are anticipated under alternative hypotheses for the two remaining comparative arms. Without taking into account the expected minimal loss of power due to interim analyses, the power in detecting the survival improvement for the remaining experimental arm (arm 2) as compared to the standard arm is at least 81.9% using a stratified log-rank test.

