15.6 Correlative Studies (CALGB 150712)

In the main treatment study, a total of 303 patients will be randomized to the standard control arm (arm A) and the remaining experimental arm (arm B or arm C, depending on the toxicity data from an initial cohort, the more toxic experimental arm will be dropped). These patients will be followed for disease progression and survival for at least 3 years after enrollment. All patients will be invited to join the correlative science substudies. Samples from consenting patients will be collected at baseline (before treatment initiation), day 21 (pre-chemotherapy), at first follow-up after completion of all protocol treatment, and at the time of disease recurrence. The laboratory data, including measures of all biomarkers described in the protocol, will be sent to the Alliance Statistics and Data Center, where the laboratory data will be merged with the clinical data and analyzed by Alliance statisticians.

Power Analysis for the First Correlative Science Substudy (Section 10.1.1):

The primary objectives of this first correlative science substudy are (i) to test whether higher-dose, accelerated radiation therapy (arm B or C) will cause a larger rise in circulating markers of endothelial damage than hyperfractionated and accelerated radiotherapy (arm A), and (ii) to determine whether the baseline biomarker profile, or changes in the profile during treatment, correlate with clinical outcome as judged by objective response rate, progression free survival, and overall survival.

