With allowance of 20% patient loss due to consent, ineligibility, and specimens of poor quality, we assume that 264 patients on arm A and 264 patients on arm B/C will provide evaluable circulating biomarkers for final analysis. With regards to the first primary objective, we assume the transform of biomarker count difference between post-treatment initiation and baseline follows approximately a normal distribution so that a 2-sample t test would be appropriate. At a 2-sided significance level of 0.05, the study has 90% power to detect a 0.274 standard deviation of cell count difference between the two treatment arms on log scale. With regards to the second primary objective, for the purpose of power analysis, the correlation of the biomarker (baseline or change scores of post-initiation of treatment against baseline) with response rate, 2-year FFS and 2-year OS will be tested for each arm using logistic regression with a single continuous predictor. At a 2-sided significance level of 0.05, the study has at least 90% power to detect a 6% increase of response rate from 80% at the mean of the biomarker to 86% at one standard deviation above of the mean. Similarly, the study has at least 90% power to detect an 11% increase of 2-year FFS from 40% at the mean to 51% at one standard deviation above of the mean, to detect an 11% increase of 2-year OS from 50% at the mean of a biomarker to 61% at one standard deviation above of the mean.

Power Analysis for the Second Correlative Science Substudy (Section 10.1.2):

The primary objective of the second correlative substudy is to evaluate the correlation of several serum markers at baseline or their changes against baseline with response rate (RR), failure free survival (FFS), and overall survival (OS) in small cell lung cancer. They include neuron-specific enolase (NSE), carcinoembryonic antigen (CEA), BB isoenzyme of creatine kinase (CK-BB), angiogenic factors Interleukin 8 (IL-8) and Vascular Endothelial Growth Factor (VEGF), stem cell factor (SCF), granulocyte-macrophage-colony stimulating factor (GM-CSF), and tumor

hypoxia marker osteopontin. The correlation tests are considered exploratory and the Type I errors will not be adjusted for multiple comparisons.

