It is assumed that 230 randomized patients (70%) on each arm will consent and provide valid measures for these biomarkers. These biomarkers are concentration in the blood. The baseline measures and the change at different time points – day 21; at first follow-up after completion of all protocol treatment; and at the time of disease recurrence – against baseline are continuous variables. For the purpose of power analysis, logistic regression with a single continuous predictor will be used to test a measure's correlation with RR, 2-year FFS, and 2-year OS, separated by study arm. At a 2-sided significance level of 0.05, the study has at least 90% power to detect a 6% increase of response rate from 80% at the mean of the biomarker to 86% at one standard deviation above of the mean. Similarly, the study has at least 90% power to detect a 12% increase of 2-year FFS from 40% at the mean to 52% at one standard deviation above of the mean, to detect a 12% increase of 2-year OS from 50% at the mean of a biomarker to 62% at one standard deviation above of the mean.

Power Analysis for the Third Correlative Science Substudy (Section 10.1.3):

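### Section 15.6: the correlative-study sizes of 264 and 230 per arm do not follow from 303 per arm, and the response-rate power stated as at least 90% is about 79% and 74% even at those sizes

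*Combined protocol and SAP*

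**What the plan says.** Section 15.6 opens from the main design: "a total of 303 patients will be randomized to the standard control arm (arm A) and the remaining experimental arm". Section 15.3 confirms that this is a per-arm number: "303 eligible patients in the standard arm and 303 eligible patients in the remaining experimental arm".

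For the first substudy, Section 15.6 says: "With allowance of 20% patient loss due to consent, ineligibility, and specimens of poor quality, we assume that 264 patients on arm A", and gives the same 264 for arm B/C. For the second it says: "It is assumed that 230 randomized patients (70%) on each arm will consent".

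Three kinds of power statement follow, all at a two-sided 0.05 level:

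- **Arm comparison, first substudy (two-sample t test):** "the study has 90% power to detect a 0.274 standard deviation of cell count difference between the two treatment arms".
- **Response rate, both substudies:** "the study has at least 90% power to detect a 6% increase of response rate from 80% at the mean of the biomarker", with 86% at one standard deviation above the mean. The method is logistic regression with one continuous predictor, run separately in each arm.
- **2-year failure-free survival (FFS) and overall survival (OS):** at least 90% power for an 11-point increase in the first substudy and a 12-point increase in the second.

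Section 5.6 narrows the pool: "Patients that are registered on CALGB 30610 after they receive one cycle of chemotherapy are NOT eligible for the companion studies".

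**The concern.** There are two separate problems. First, the evaluable numbers are not the stated percentages of the stated base. Second, the response-rate power looks too high. At an 80% response rate there are few non-responders, so a 6-point rise per standard deviation is hard to detect in one arm of about 250 patients.

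Section 15.6 lists the relation of biomarkers to response among the primary objectives of both substudies. A reader who believes the miss risk is at most 10% will give a null result more weight than it can bear.

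**Working it through.** **Inputs.** From Sections 15.3 and 15.6: 303 per arm; 20% loss (first substudy) and 70% participation (second); 264 and 230 evaluable per arm; two-sided 0.05; response 80% at the mean and 86% at +1 SD; difference of 0.274 SD for the arm comparison. Assumption: the biomarker is standard normal after scaling.

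**Sizes.**

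- 0.80 × 303 = 242.4, against 264 stated (264/303 = 87%).
- 0.70 × 303 = 212.1, against 230 stated (230/303 = 76%).
- Working back: 264/0.80 = 330 and 230/0.70 = 329. Both stated sizes fit a base of about 330 per arm.

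**Response-rate power.** Odds at the mean are 0.80/0.20 = 4 and at +1 SD 0.86/0.14 = 6.143. The odds ratio per SD is 1.536 and the log odds ratio is 0.429. For one normal covariate,

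power = Φ( √(n·p(1−p)) × |log OR| − 1.960 ), with p = 0.80.

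At n = 264: √(264 × 0.16) = 6.499; 6.499 × 0.429 = 2.788; 2.788 − 1.960 = 0.828; Φ(0.828) = 79.6%. The other sizes follow the same way. The formula was checked by simulation (6,000 to 8,000 runs per size):

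| Patients in the arm | Formula | Simulation (Wald / likelihood ratio) | Stated |
|---|---|---|---|
| 264 (first substudy, as stated) | 79.6% | 78.5% / 79.2% | at least 90% |
| 230 (second substudy, as stated) | 74.0% | 73.5% / 74.5% | at least 90% |
| 242 (80% of 303) | 76.1% | 75.2% / 76.1% | – |
| 212 (70% of 303) | 70.5% | 69.2% / 70.4% | – |
| 303 (whole arm) | 84.8% | 84.4% / 85.0% | – |

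Size for 90% power: (1.960 + 1.282)² / (0.16 × 0.429²) = 357 per arm, more than the arm contains.

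**Can the stated 90% be reproduced?** The document names no formula. An older approximation for logistic regression (Whittemore type), with the event rate entered as 0.80, returns 95.5% at 264 and 92.6% at 230. With the same outcome coded as non-response (0.20), it returns 72.7% and 66.5%. True power cannot depend on which outcome is called the event, and simulation contradicts the higher figures. That this was the source is an inference.

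**Response rate at +1 SD detectable with 90% power (formula).** About 86.9% at 264, 87.3% at 230, 87.1% at 242 and 87.5% at 212. Simulated power for the last two is 89% to 90%.

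**Arm comparison.** The 90%-detectable difference is (1.960 + 1.282) × √(2/n): 0.282 SD at 264 and 0.295 SD at 242. The stated 0.274 SD needs 280 per arm. Its power is 88% at 264 and 85% at 242.

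**FFS and OS.** Simulated power is 93% for both at 264, and 94% and 95% at 230. At the recomputed sizes it is 91% and 92% (242, 11-point effect) and 92% and 93% (212, 12-point effect). These statements stand.

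**The case against.** **The base may be larger than 303.** The 20% loss includes ineligibility, whereas Section 15.3 describes the 303 as eligible patients after a 5% allowance. Applied to patients before that allowance, 303/0.95 = 319 gives 255 and 223, within about 3% of the stated sizes. But Section 15.6 itself takes 303 as randomized, and its 70% is of randomized patients. The 5% in Section 15.3 covers patients who cancel or are ineligible for randomization. Even at 255 and 223 the response-rate power is only 77% to 78% and 71% to 73%. The document should state its base, but no reading rescues the power claim.

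**Pooling would restore the power.** With both arms combined, the formula gives 97.6% (n = 528) and 95.7% (n = 460). The plan for analysing response does not expressly confine the test to one arm. However, both power statements say that the calculation is by arm, so the stated figures are wrong for the test they describe.

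**The tests are exploratory and the shift is small.** Section 10.1.1 calls the first substudy's objectives exploratory, and Section 15.6 says the same of the second's tests. The 90%-detectable response rate moves by only 1 to 1.5 points, and nothing in the document says that a null result will be read as no effect. All of this stands and limits the weight of the point, not its truth.

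**The t test is a near miss.** This is fair: 88% against 90% at 264 is minor. It matters mainly because it becomes 85% at 242.

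**The same effect at two sizes is no contradiction.** Also fair, since both statements say at least 90%. The fault is that neither size reaches it.

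**Conclusion.** The concern holds. The sizes of 264 and 230 exceed what 303 per arm yields by about 22 and 18 patients. The response-rate power is overstated by at least 10 points at 264 and 16 at 230, and by about 14 and 20 points at 242 and 212. The chance of missing the stated effect is therefore about 20% to 30%, not at most 10%, and full participation in an arm would not deliver the claim.

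This rests on a normally distributed biomarker, a two-sided 0.05 test and analysis within each arm; the last two are the document's own terms. The sizes are upper limits, because patients registered after one cycle are excluded and the document gives no count of them. The survival-related biomarker statements and the trial's primary analysis are not affected.

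**What to change.** In Section 15.6:

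1. State the base explicitly, and give the evaluable numbers as at most 242 (first substudy) and 212 (second) per arm, before removing patients registered after one cycle. Say how many such patients are expected.
2. For response rate, either report about 75% and 70% power for the rise from 80% to 86%, or give the 90%-power effect as 80% to about 87% (n = 242) and 80% to about 87.5% (n = 212).
3. For the arm comparison, replace 0.274 SD with about 0.295 SD.
4. Leave the FFS and OS effects unchanged, with the corrected sizes.

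The cost is a text correction and less favourable stated power. No extra patients, samples or analyses are needed.

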In addition to analyzing the small cell lung cancer specific biomarkers as described above, we will also include two additional groups of proteins. First, we will assess factors that we have already established to be modulated by radiotherapy or endothelial damage, including VEGF, soluble VEGFR-2, and E-selectin [53-55]. The second set of factors will be proangiogenic cytokines that may contribute to resistance by promoting the proliferation and survival of tumor endothelial cells. First, several selected proangiogenic cytokines

known to play a role in angiogenesis in lung cancer, including VEGF, basic fibroblast growth factor (bFGF), transforming growth factor α (TGF- α), and interleukin-8 (IL-8).

Objectives: The objectives of the correlative studies for small cell specific circulating markers are:

1. To investigate the value of the published markers specific to small cell lung cancer in the large phase III clinical study setting. We will analyze the baseline biomarker profile, changes in the profile during treatment at the time of recurrence to correlate with the response rate, progression free survival, and overall survival of these patients.
2. To compare the differences in the biomarker profile between the two treatment arms.

Hypotheses

1. Circulating biomarkers may have prognostic or predictive value of small cell lung cancer.
2. The differences in circulating biomarkers between the two treatment arms may reveal information correlating with efficacy of treatments.

Method for the ELISA Assay

ELISA is a standard laboratory analytical method for protein quantification in the plasma or serum (R&D Systems, Minneapolis, MN). This assay requires a significant volume of sample (100-200 μ l) for each biomarker. The ELISA assay has high sensitivity and high precision, and thus has been the standard assay of cytokine measurement.

10.1.3 ProGRP as a Marker to Monitor the Response to Therapy and for the Prediction of Relapse Following Therapy

The goal of this correlative study is to evaluate the performance of proGRP as a biomarker in SCLC lung cancer. In addition, this study will provide an opportunity to better understand the role proGRP to monitor the response to therapy and the relapse following therapy.

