Descriptive statistics will used to characterize biomarker count or distribution over time and changes against baseline. The change of biomarker count or mean between treatment arms will be tested using a 2-sample t test on a transformed scale such as the use of t test is appropriate. If the normal assumption is violated, Wilcoxon rank sum test, a nonparametric test, will be used. As supplementary analysis, the difference of biomarker count and mean change will be modeled using generalized linear model using appropriate link function.

The correlation of the baseline measure or the change of the biomarker measure relative to baseline with response rate (RR) will be evaluated using logistic regression [86] with and without adjusting for significant confounding variables at baseline. The correlation of the biomarker with failure free survival (FFS) and overall survival (OS) will be evaluated using Cox's proportional hazard model [87] for time to event data without and with adjusting for confounding variables. These analyses will reveal whether the baseline biomarker or its change against baseline during treatment is predictive to RR, FFS, or OS, or whether the correlation is dependent on which treatment is given. In the pooled analysis of all patients on the treatment arms, the interaction between treatment and baseline or change score of the biomarker will be tested to evaluate the predictive value of the biomarker to different treatments.

If a continuous biomarker is significantly correlated with FFS or OS, an optimal threshold for classifying patients into subgroups will be identified by searching the dichotomized level of the continuous predictor at which yields the maximal log rank statistic. Both the raw p-value from the log rank test as well as the adjusted p-value from the maximal log rank statistic [88], which takes the randomness of the maximally selected cutoff point into account, will be provided. Kaplan-Meier curves [89] will be used to describe survival difference for different subgroups of patients classified by predictive biomarker at its optimal cutoff point.

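### The second correlative substudy includes biomarker change at disease recurrence among the measures tested against response, FFS and OS, with a sample size and power that cannot apply to that measure

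*Combined protocol and SAP*

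**What the plan says.** Section 15.6, in the power analysis for the second correlative substudy, treats as continuous measures the baseline value and its change at three later points: day 21, then "at first follow-up after completion of all protocol treatment; and at the time of disease recurrence". The next sentence gives the model assumed for the power calculation, applied to each arm on its own: "logistic regression with a single continuous predictor will be used to test a measure's correlation with RR, 2-year FFS, and 2-year OS, separated by study". The sample size is common to all measures: "It is assumed that 230 randomized patients (70%) on each arm will consent and provide valid measures for these biomarkers". On that basis it makes this claim for response, the second rate being the one expected one SD higher: "the study has at least 90% power to detect a 6% increase of response rate from 80% at the mean of the biomarker to 86" (per cent). For FFS it claims "at least 90% power to detect a 12% increase of 2-year FFS from 40% at the mean to 52% at one standard deviation", and it gives the same power for 2-year OS, with 50% rising to 62%.

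The objective in Section 10.1.2 has the same content. The profiles to be analysed include "changes in the profile during treatment at the time of recurrence to correlate with the response rate, progression free survival, and overall survival".

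The Analytic Methods in Section 15.6 use logistic regression for response and Cox models for FFS and OS. They describe the aim as learning if the starting value is informative, "or its change against baseline during treatment is predictive to RR, FFS, or OS".

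Two definitions matter. Section 15.1.3 counts FFS from randomisation to progression or death, whichever is first. Section 13.4 records best overall response only up to progression or recurrence.

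**The concern.** A recurrence sample exists only in patients who have recurred, and recurrence is an FFS event. A model that relates its value to FFS therefore measures the predictor at the outcome. For response, the outcome is fixed before the predictor is drawn. For OS counted from randomisation, every patient in the model has survived to recurrence, and that survival time is credited to a value not yet observed.

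An association from such a model could not be read as prognostic or predictive. The plan also acts on these associations. Under the Analytic Methods, a continuous biomarker significantly correlated with FFS or OS goes into a search for the cut-point that maximises the log-rank statistic, followed by Kaplan-Meier curves for the resulting groups. An artefact of sampling time could thus be reported as a threshold for classifying patients. Finally, the 230 per arm is stated as if every measure, including this one, were available in all of those patients.

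**Working it through.** **1. The plan's own power figure.** Inputs from Section 15.6: n = 230 per arm, two-sided 0.05, power 90%. Let P be the event rate at the biomarker mean and b the log odds ratio per SD. The Hsieh (1989) formula for logistic regression with one continuous predictor is

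n = (z_a + exp(−b²/4)·z_b)² × (1 + 2Pd) / (P·b²), with d = [1 + (1 + b²)·exp(5b²/4)] / [1 + exp(−b²/4)].

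For 2-year FFS, b = ln[(0.52/0.48)/(0.40/0.60)] = ln 1.625 = 0.4855.

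| Outcome | Odds ratio per SD | n for 90% power | Power at n = 230 |
|---|---|---|---|
| Response, 80% to 86% | 1.536 | 210 | 0.926 |
| 2-year FFS, 40% to 52% | 1.625 | 224 | 0.909 |
| 2-year OS, 50% to 62% | 1.632 | 199 | 0.938 |

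The stated figure reproduces for any measure that 230 patients per arm actually have. One side remark: the response figure depends on the formula. Hsieh (1998) and simulation both give 0.74 at n = 230, while FFS and OS stay at about 0.95 or above. That is a separate matter.

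**2. How many patients could have a recurrence value.** Take 40% as the overall 2-year FFS rate (the plan gives it at the biomarker mean).

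- Failures by 2 years: 230 × (1 − 0.40) = 138 per arm.
- Further assumptions: exponential FFS with λ = −ln(0.40)/2 = 0.458 per year; uniform accrual over 6 years (length from Section 15.3); minimum follow-up of 2.5 years (Section 15.3) or 3 years (opening of Section 15.6).
- Proportion still failure-free at analysis, for minimum follow-up f: [exp(−λf) − exp(−λ(f + 6))] / (6λ).
- f = 2.5: (0.318 − 0.020)/2.749 = 0.108, so 230 × 0.892 = 205 ever fail, of whom 205 − 138 = 67 fail after 2 years.
- f = 3: (0.253 − 0.016)/2.749 = 0.086, so 230 × 0.914 = 210 ever fail, of whom 210 − 138 = 72 fail after 2 years.

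These are ceilings, because an FFS failure can be a death without recurrence and a sample can be missed. If 70% to 100% of failures give a recurrence sample (an assumption; the plan gives no figure), the usable number is about 0.70 × 205 = 144 up to 210 per arm.

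**3. What each outcome looks like among those patients.**

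- *FFS.* A recurrence sample at or before 24 months always belongs to a 2-year failure (up to 138), and a later one always to a 2-year success (up to 67 to 72). The date fixes the outcome whatever the biomarker shows. In the Cox model for FFS, the covariate is measured at the event time, and patients who never recur have no value.
- *Response.* Section 13.4 closes the window at progression or recurrence, so the outcome precedes the predictor.
- *OS.* Recurrence is not death, so the sample does not fix 2-year survival. The fault is restriction to patients who lived to recur, with time counted from randomisation.

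Recomputing power at 144 to 210 would not repair this, because the tested association has no useful interpretation for FFS or response.

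**The case against.** The best defence is that the 2-year logistic model is only a device for the power calculation. The operative methods use Cox models for FFS and OS and speak of change during treatment, and a recurrence sample would ordinarily come after treatment. The Section 10.1.2 sentence seems to lack a conjunction and speaks of correlating, not predicting. The recurrence sample also has legitimate uses in the plan, such as describing change over time. And Section 15.6 labels the tests exploratory.

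Part of this stands. The 2-year logistic model should not be taken as the final analysis, and the exploratory label limits the consequence. But the during-treatment phrase occurs in a sentence about what the analyses will reveal. The sentences that specify the models refer to change relative to baseline without limiting the time point, and nothing excludes the recurrence sample. A Cox model without a landmark or time-dependent covariate has the same fault for FFS. The exploratory label is attached to the absence of multiplicity adjustment; it does not settle the timing of a predictor.

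A reader might infer more than the documents support:

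- *That all three outcomes are circular.* Only FFS is. Response is a matter of time order, OS of selection and immortal time.
- *That the recurrence sample carries no information on 2-year FFS.* The outcome is constant only among recurrences within 2 years; later recurrences are 2-year successes. The trouble is that the date, not the biomarker, separates the two groups.
- *That the power statement is valid only for baseline values.* The calculation reproduces at n = 230 for any time point with that many valid samples.
- *That the day-21 change also needs a landmark.* The documents give no figure for failures before day 21, and no bias there has been shown.

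**Conclusion.** The point holds: read literally, Sections 10.1.2 and 15.6 relate the recurrence change to response, FFS and OS, and that is wrong as written. The FFS analysis is circular, the response analysis reverses time order, and the OS analysis is conditioned on surviving to recurrence.

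The 230 per arm cannot apply to this measure. At most about 205 to 210 per arm would ever have an FFS failure, and fewer a recurrence sample. This ceiling rests on 40% as the overall 2-year FFS, exponential FFS, uniform 6-year accrual and 2.5 to 3 years' minimum follow-up. The logical fault does not depend on those assumptions.

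Severity is low. The tests are exploratory, and the primary OS comparison, its interim monitoring and the trial's sample size are unaffected.

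**What to change.** Amend the objective in Section 10.1.2, and the second-substudy power text and the Analytic Methods in Section 15.6:

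1. Remove the recurrence change from the response, FFS and OS models and from the power statement.
2. State that these models use baseline values and on-treatment or first-follow-up changes. For the first post-treatment sample, use a landmark at the draw in the FFS and OS models: include patients still at risk then and count time from that point.
3. Analyse the recurrence sample descriptively, as a paired change from the last sample before recurrence, or against survival counted from recurrence. Section 6.3.1 already schedules draws at each follow-up visit and at recurrence.
4. As far as this point goes, the stated power may stay for baseline, day 21 and first follow-up, on the written condition that 230 valid samples per arm exist at each.

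The plan already has a pattern to follow: the ProGRP substudy compares marker change with disease status by sequential pair, and groups patients for PFS by baseline, post-cycle and first post-treatment values. The cost is wording only, with no new samples, visits or patients.
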